For this research study subjects will donate blood sooner than would be done in routine clinical practice. Volunteers, however, should not exhibit deleterious levels of anemia during the study since a hemoglobin of at least 12.5 g/dL will be required before donating blood at any time. Based on previous studies we expect the lowest hemoglobin levels to be approximately 11-12 g/dL (hematocrit of 33-36%) after donation. Volunteers will be told that while anemia of this level is not dangerous, they may feel fatigued, be more likely to experience dyspnea on exertion, and have decreased exercise performance until their hemoglobin level is increased on the transfusion day. In order to minimize these potential effects they will be advised to refrain from moderate or heavy exercise during these times when they may have mild anemia.

Subjects will be informed that during the study they may take a multivitamin but they should not take iron supplements.

3. Risks of blood transfusion (Wednesday visit during week 6 of each cycle):
 - a. During blood donation bacteria may be introduced into the donated unit because it is impossible to completely sterilize the skin through which venipuncture occurs. Also, donors may have asymptomatic infection of bacteria in the blood stream due to recent dental procedures or developing illness. The reported rates for allogeneic RBC unit bacterial contamination range from 0.01% to 0.27%. As the subjects in this study have allogeneic donor criteria applied to them, this would be a fair estimation of bacterial contamination risk. If the subject experiences fever within 2 days after donating their unit of whole blood, they will be asked to call [name] at [name]. The subject may be excluded from continued participation in the study. If the blood is stored longer than 14 days prior to transfusion, a sample of the stored blood will be tested for the presence of bacteria 7 days before re-infusion. If tests are positive for the presence of bacteria, the subject will be notified and their participation in the study will not continue.
 - b. Additional transfusion reactions, such as chills, fever, drop in blood pressure, transfusion associated circulatory overload (TACO) or pulmonary edema, and shock may also occur. There may also be allergic reactions such as hives, rashes, or (very rarely) anaphylactic reactions that could result in death.
 - c. The subject may experience pain around the IV site or in the arm with the IV. Investigators will select the largest available vein in the forearm or antecubital fossa to minimize pain during blood infusion.
 - d. Mistransfusion, arising from errors in unit labeling, component preparation or other clerical errors occurs in 1:16,000 - 1:25,000 autologous donations. To minimize the risk of mistransfusion, which in the worst possible case may trigger a fatal or serious acute reaction, multiple safeguards to prevent this are written into our study protocol and include the following:
 - i. multiple sample and bag identification checks
 - ii. 2 persons will confirm the subject's identity with the stored RBCs, using established hospital approved standard Stony Brook Hospital transfusion procedures
 - iii. a standard crossmatch will be performed between the subject's stored donated unit and a fresh sample of the subject's blood (if an antibody is found, an extended crossmatch will be performed)
 - iv. only one subject will be transfused on a given day to minimize risks

- v. the research subject will be asked to review their signature on the labels for their autologous units to confirm they are receiving their own blood
4. Risks associated with exercise (VO₂ max) testing: The most common complaint from those performing the exercise test on a bicycle is thigh pain during the test. In healthy volunteers, the likelihood of death or a serious complication, e.g. sustained arrhythmia, is low, but not impossible. The following is language from a recent publication:
Risks of Physical Activity, Exercise Training, and Exercise Testing
*Recommendation 1: Maximal exercise stress testing is associated with a very low risk of fatal and non-fatal cardiac events in either healthy asymptomatic or clinical populations. In healthy, asymptomatic individuals, the respective incidences of fatal and nonfatal events are approximately 0.3-0.8/10,000 tests and 1.4/10,000 tests (Level 3, Grade B).*⁵¹
 5. Risks associated with loss of protected health information: As with any participation in a research study there is a small chance that a loss of confidentiality could occur, but our use of standard risk management procedures will minimize this risk.

Adequacy of Protection Against Risks

Numerous aspects of the study procedures are designed to minimize potential risk to subjects. Most of these procedures have been used by us in previous studies of blood donation/transfusion including our pilot study and our TASER study²⁴ and maximal exercise testing.^{25,26}

1. Safety Monitoring Plan: We will record and analyze both expected and unexpected adverse events in order to monitor for and minimize potential risks to human subjects. Adverse events that occur during any study procedure will be collected and reported to the IRB, NIH, and FDA as applicable. The Principal Investigator will review serious and non-serious AEs on a rolling basis as well as in aggregate on a monthly basis. Given the long standing safety of VO₂ max testing as well as blood collection and transfusion studies (many removing far larger volumes of RBCs) we do not expect to see a significant number of adverse events. In our recent pilot study and TASER study²⁴ no adverse events were observed.
2. Protection from Loss of Confidentiality: Study records that identify the subject will be kept confidential as required by law. All participants will be given a unique code. The key to the code will be kept in a locked file in the Study Coordinator's or [name] office. All computer records will be secured with password protection and appropriate firewalls will ensure confidentiality and safety of all patient materials and data. Study documents will be kept in a locked file cabinet in either the Study Coordinator's or [name] office. Source documents sent to the NIH and FDA as applicable will have all direct identifiers masked with opaque black ink. Except when required by law, the subject will not be identified by name, social security number, address, telephone number, or any other direct personal identifier in study records disclosed outside of Stony Brook University. The results of this research study may also be presented at meetings or in publications; however, identity will never be disclosed in those presentations. In no way will any subjects' name be used in any published form. Medical records that identify the subject and the consent form may be inspected by the FDA, other regulatory agencies, and the Institutional Review Board (IRB), in order to meet federal and state regulations. If the volunteer's research record is reviewed by any of these groups, they may need to review the entire medical record. The primary purpose of such review is to ensure the protection of the rights and welfare of the human subjects.
3. Protection from Risks associated with blood donation: Our eligibility criteria are designed in part to minimize the likelihood of individuals who may be at higher risk for blood donation. For example, individuals with anemia, medical problems, or total blood volume less than 4,500 will not be eligible. In addition, we will exclude individuals with a history of fainting or similar adverse reactions during blood donation. Subjects will only be allowed to donate blood (2 unit apheresis collection) if their pre-donation hemoglobin is at least 12.5 g/dL measured using SBUH Blood Bank's standard FDA approved device. A hemoglobin of 12.5 is consistent with the following guideline published by AABB: "*The minimum acceptable hemoglobin for both men and women is defined by the FDA as 12.5 g/dL, with the essentially equivalent hematocrit requirement of 38%.*" Per standard SBUH Blood Bank procedures, all volunteers will be offered some food and liquid after donation and will be encouraged to sit for 30 minutes after donating. The SBUH Blood Bank has routine emergency resuscitation equipment in the collection area, which further minimizes risk. In addition, volunteers will be told that while the mild anemia they are expected to have after blood collection is not dangerous for fit healthy volunteers, they may feel fatigued, be more likely to experience dyspnea with exertion, and have decreased exercise performance until their

hemoglobin level is increased on the transfusion visit in week 6 of each cycle. They will be advised to refrain from moderate or heavy exercise during the weekend prior to week 6 and during week 6 of each cycle. Since subjects will agree to this exercise restriction at the time they provide informed consent, we believe few to none of them will drop out due to anemia symptoms or restricted exercise during this short (9 days) period of time each cycle. Subjects are unlikely to have significant symptoms of anemia during light exercise, e.g. walking.

4. Protection from Risks associated with blood transfusion: To minimize risks, the following study procedures will be used:
 - a. If the subject experiences fever within 2 days after donating their unit of whole blood, they will be asked to call [name] at [contact]. The subject may be excluded from continued participation in the study.
 - b. If the blood is stored longer than 14 days prior to transfusion, a sample of the stored blood will be tested for the presence of bacteria 7 days before re-infusion. If tests are positive for the presence of bacteria, the subject will be notified and their participation in the study will not continue.
 - c. During blood transfusion (which will occur in a Health Sciences Center lab or the SBUH Blood Bank), subjects will be monitored by an experienced RN study coordinator and one of the physician investigators will be either at the bedside or immediately available. We will monitor temperature, blood pressure, ECG, and pulse oximetry in order to detect possible transfusion reactions. In addition, consistent with our previous pilot study, each RBC unit will be administered over 60 minutes to minimize the likelihood of transfusion associated circulatory overload (TACO) or pulmonary edema, which is unlikely in healthy, fit subjects.
 - d. Investigators will select the largest available vein in the forearm or antecubital fossa to minimize pain during blood infusion.
 - e. To minimize the risk of mistransfusion, which in the worst possible case may trigger a fatal or serious acute reaction, multiple safeguards to prevent this are written into our study protocol and include the following:
 - i. multiple sample and bag identification checks
 - ii. 2 persons will confirm the subject's identity with the stored RBCs, using standard Stony Brook Hospital transfusion procedures
 - iii. a standard crossmatch will be performed between the subject's stored donated unit and a fresh sample of the subject's blood (if an antibody is found, an extended crossmatch will be performed)
 - iv. only one subject will be transfused on a given day to minimize risks
 - v. the research subject will be asked to review their signature on the labels for their autologous units to confirm they are receiving their own blood

5. Protection from Risks associated with exercise (VO₂ max) testing: To minimize risks of VO₂ max testing, we will only enroll healthy, habitually exercising, non-obese subjects between 18-40 years of age. This represents a group at very low risk for adverse events. Nevertheless, during testing all subjects will be monitored by a physician with appropriate monitors and emergency resuscitation, e.g. defibrillator, will be immediately available. All exercise tests will be performed in a co-investigator's lab in the Health Sciences Center of Stony Brook University Hospital. Additional safeguards include a screening ECG to rule out long QT interval, and spirometry to rule out occult pulmonary disease. In addition, we will use standard criteria to terminate the VO₂ max test.

Termination Criteria for VO₂ max Test

1. Subject fatigue or subject request for any reason
2. Inability to maintain the prescribed cadence (75-80 rpm) at the current work rate
3. Onset of chest pain or equivalent angina symptoms, such as unusual or extreme shortness of breath, or signs of poor perfusion, as noted by the subject or determined by the monitoring physician
4. Sequential ventricular beats of two or more (i.e., 2 beats of ventricular tachycardia)
5. New onset of sustained (>15 seconds) atrial fibrillation, supraventricular tachycardia (SVT), or other supraventricular tachyarrhythmias
6. Development of new left bundle branch block (LBBB)
7. Systolic blood pressure >240 mm Hg, or diastolic blood pressure >130 mm Hg
8. Progressive decrease in heart rate or systolic blood pressure during increasing exercise intensity accompanied by clinically significant signs or symptoms
9. Second-degree Type II or third-degree heart block.

Potential Benefits of the Proposed Research to the Subject and Others

There is no benefit to the subject for participating in this study. There may be a benefit to future patients based on results from this study.

Importance of the Knowledge to be Gained

The proposed study is significant for several reasons: 1) We believe that the proposed study is likely to confirm our very encouraging preliminary data, showing that the oldest RBCs allowed by FDA regulations (42 days) are inferior to 7 day RBCs in a functional assay of oxygen delivery. This is important scientifically since, to our knowledge, no studies have definitively shown that storage duration can affect RBC function, i.e. oxygen delivery; 2) The proposed study is also significant because it may shed light on why the RECESS and ABLE outcome trials, comparing young and “middle-aged” RBCs were negative. We hypothesize that 28 day RBCs are not inferior to 7 day RBCs, which are exactly the median ages of storage for the two study arms in RECESS.¹¹ 3) Finally, we suggest that this model holds promise as a rigorous and quantitative in vivo functional assay of RBC function, which is an unmet need for future RBC transfusion research as identified by NHLBI and others.

Risk Benefit Assessment

We believe that the information to be gained from this study is reasonable compared with the small risks of transfusion of autologous blood to healthy volunteers and VO₂ max testing in healthy volunteers.

LITERATURE CITED

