Blood Transfusion: Early studies (1976, 1980) in healthy volunteers failed to show an improvement in VO_2 max after transfusing liquid RBCs, possibly due to the low quality of the stored RBCs.^{46,47} In contrast, later studies that transfused at least 2 units of cryopreserved, deglycerolized autologous RBCs to healthy volunteers showed consistent increases in VO_2 max, even if pre-transfusion Hb was as high as 16 g/dL.^{44,45,48-50} In other words, the increase in VO_2 max does not require anemia at baseline to show improvements in VO_2 max. For example, in 8 volunteers, Celsing et al removed 450 mL of whole blood 5 times, resulting in lower VO_2 max at A (anemia; figure right).⁴⁸ One unit of cryopreserved RBCs was transfused on visits 1, 2, 3, and 4 over several weeks, resulting in a stepwise increase in both hemoglobin and VO_2 max (L/min). As expected, control subjects (n=8, dotted line) showed no change in hemoglobin or VO_2 max.

Our preliminary data are consistent with the above studies, since we showed a predictable increase in VO_2 max after transfusion with 2 units of 7-day RBCs. None of these previous studies, however, determined whether storage duration impairs the ability of the RBCs to deliver oxygen, which was the focus of our pilot study and will be characterized further in the proposed study.

D. RESEARCH DESIGN AND METHODS

[figure not shown]
This is a single-center, randomized, partially blinded study.

1) Overview

After consent and screening the study interventions last 6 weeks and consist of 2 phlebotomy visits at Stony Brook hospital and transfusion with 2 units of autologous AS-3 RBCs that are either 7-, 28-, or 42-days old. Subjects will be randomized (1:1:1) to either cycle A (7 day RBCs), cycle B (28 day RBCs, or cycle C (42 day RBCs).

During week 6 of each cycle, subjects will have 3 study visits consistent with the pilot study we just completed.

- On Monday subjects will have a VO_2 max test.
- On Wednesday, they will be transfused with 2 units of autologous RBCs (each over 1 hour), followed by a VO_2 max test 2 hours later to assess the “acute” effects of transfusion (intravascular volume + RBC mass), which is a secondary endpoint of the proposed study.
- On Friday, they will have a VO_2 max test, which is compared with the baseline VO_2 max result (Monday) in order to calculate a delta VO_2 max related to transfusion (primary endpoint), avoiding potential confounding from acute intravascular volume effects.

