Removal of waste unit(s): During each cycle, subjects will also have a second visit to Stony Brook. For example, Cycle A has 2 units removed at Week 0, Cycle C has 2 units removed at Week 5. These units are removed for 2 reasons: 1) to maintain blinding for the 7- vs 42-day RBC comparison since subjects will not know whether they are receiving their 7- or 42- day RBCs; and 2) to induce mild anemia (projected Hb 11-12 g/dL), which, while still extremely safe, may enhance increases in VO_2 max from transfusion in order to detect more robust differences between study arms. We have numerous safeguards in place to protect human subjects (see Human Subjects section).

Blinding: We cannot fully blind Cycle B (28-day RBCs). However, we plan to partially blind the subject by informing them that they may receive either 2 units of 28-day RBCs or 1 unit of 28-day RBCs and 1 unit of 7-day RBCs. This “deception” should be allowed since it is inconsequential to the subjects, as they will already have agreed to receive 7- and 42-day RBCs in other cycles, and is merely done to improve blinding of the study. Notwithstanding the above, we believe this strategy is a reasonable compromise since VO_2 max is a quantitative measurement and subjects are motivated fit athletes who, in our experience, exercise to exhaustion.²⁵⁻³⁵ Furthermore, subjects are not likely to have preconceived ideas/bias about the efficacy of

28-day RBCs. In cycles A and C, 2 units of blood will be removed 7 days before the transfusion week. However, for cycle B, only 1 unit of blood will be removed 7 days before the transfusion week because their initial 2 unit phlebotomy will be at day 28 and not at day zero. They will have had 14 fewer days to recover hemoglobin compared to cycles A and C. Based on our estimates of RBC mass removal and restoration (synthesis), we anticipate that this will result in a pre-transfusion Hb that is similar to cycles A (7-day) and C (42-day).

2) Research Site

All study procedures will be completed at a single center, Stony Brook University Hospital.

3) Study Sample

Consistent with our pilot data, qualified volunteers will be enrolled at Stony Brook University Hospital.

4) Screening

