- xi. Recent history of blood donation: a) Single whole blood unit donation within the past 8 weeks; b) Double RBC donation by apheresis within the past 16 weeks; or c) Plasma donation by apheresis within the past 4 weeks
- xii. Inadequate RBC mass based on TBV <4500 ml (above) or screening Hb <14.0 g/dL

Screening tests (performed after consent is obtained): The following will be performed to confirm eligibility and optimize the safety of subjects: 1) written questionnaires that provide written confirmation of eligibility for blood donation and confirm appropriateness for exercise testing (PAR Q+ questionnaire);⁵¹ 2) hemoglobin must be ≥ 14.0 g/dL; 3) hemoglobin A1c to rule out diabetes; 4) Sickledex to rule out sickle trait or anemia; 5) ECG to rule out prolonged QTc; 6) height and weight to calculate and confirm required total blood volume (above); 7) spirometry to rule out undiagnosed pulmonary disease; and 8) serum hCG test if female

Subjects will be informed that during the study they may take a multivitamin but they should not take iron supplements.

5) Procedures

Blood Donation, Processing, and Storage (Visit B on Day 0, Visit C on Day 35)

We will use the same procedures successfully used in our recently completed pilot study and our TASER study.²⁴ Stony Brook's Transfusion Services is registered and licensed by the FDA and accredited by the American Association of Blood Banks. [name], medical director of Transfusion Services, is a co-Investigator this study.

After passing a written screen at Stony Brook University Hospital's Blood Bank, 2 units of RBCs will be collected in CP2D via venous apheresis using a Trima Accel® Automated Blood Collection System: (<http://www.caridianbct.com/location/emea/products-and-services/Pages/trima-accel-collection-system.aspx>). Blood will be processed by technicians at this center using standard techniques. All RBCs will be leukoreduced (pre-storage), tested for all required infectious diseases, stored in AS-3 additive solution. AS-3 RBCs will be used since apheresis products collected by Trima Accel® have only been validated for AS-3. There are no data to suggest that our results would not be generalizable to AS-1 or AS-5 RBCs. Before every blood donation, each subject's hemoglobin will be measured, and only those with a value ≥ 12.5 g/dL will be allowed to donate.

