Each RBC unit will be weighed, and its volume will be calculated according to the Donor Center's standard formula: red cell volume (mL) without AS-3 = product weight/1.08.

RBC units will be stored in the blood bank under standard conditions (1°C -6°C) and under the supervision of its medical director ([name], Co-Investigator).

MONDAY of Week 6: VO₂ max Test (Baseline)

During week 6 of each cycle, the VO₂ max test on Monday will serve as the "baseline" for changes in VO₂ max measured on Friday (primary endpoint) and Wednesday (secondary endpoint) of that same week. Although we are targeting mild anemia for this visit (Hb 11-12 g/dL), it is probably not critical that we achieve a certain hemoglobin level before transfusion since previous studies have shown increases in VO₂ max for a very wide range of Hb levels, i.e. up to 16 g/dL.^{44,45,48-50}

WEDNESDAY of Week 6: Blood Transfusion and VO₂ max Testing

We will use the same procedures for transfusing autologous stored RBCs that we used successfully in our recently completed pilot study and TASER study.²⁴ Procedures (details below) have been designed to optimize safety of research subjects.

Before the subject's visit, a sterile welding device will be used to remove a small aliquot from each RBC unit. This aliquot will be sent to Stony Brook Hospital's Microbiology Laboratory for culture to rule out potential bacterial contamination of a stored unit. Based on *in-vivo* viability at 24 hours after transfusion,⁵² we anticipate that transfusion of 100% of 42-day RBCs, 95% of 28-day RBCs, and 85% of 7-day RBCs, will generally compensate for differences in post-transfusion 24-hour viability. In order to confirm that this adjustment is appropriate, we will measure the Hb levels for each subject before and after transfusion, and 2 days later (Friday visit) to ensure that there are no differences in RBC mass that could confound the results. In the unlikely event that this is an issue, our statistician can adjust for this potential interaction.

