To minimize variability in VO_2 max testing procedures, the same facilitator ([name]- Study Coordinator) will be present at every test. To further minimize variability, subjects will be required to avoid moderate or heavy exercise the weekend before week 6 and during the week of testing (week 6), which will eliminate the risk for confounding from recent strenuous exercise, e.g. a 10-mile run the day before testing.

Additional Measurements During VO_2 max Testing

On 2 of the visits for VO_2 max testing (Monday and Friday for our primary endpoint), peripheral blood Hb will be measured before each VO_2 max test to confirm that our strategy for ensuring similar RBC mass between

study arms (7-, 28-, 42-days) has been effective. If necessary our statistician can correct for a possible interaction.

Subject Payment

Subjects will be paid for each study visit that they complete: \$50 for completing screening visit, \$50 for completing each of the two blood donation visits, \$50 for completing the day 40 exercise test visit, \$150 for completing the transfusion and exercise test visit and \$350 after completing the final visit of exercise testing

E. STATISTICS

Randomization and Allocation Concealment: The pattern randomization scheme will be generated using a computer algorithm. Transfusion Services personnel will assign each subject to an administration sequence (above) using a sealed envelope technique. Subjects will be randomized to receive 7-, 28- or 42-day-old blood at the time of their enrollment.

Statistical Analyses: All analyses will be conducted by the team's biostatistician ([name]). Summary statistics, including 95% confidence intervals, will be reported on all demographic and outcome data collected, including all multiple hemoglobin and VO₂ max measures.

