- The **primary outcome** of this study is the proportional change from baseline in VO₂ max from Monday to Friday of week 6, after receiving 7-day or 42-day old blood on the Wednesday of Week 6. We hypothesize that transfusion of RBCs stored for 42 days are less effective at increasing oxygen delivery than RBCs stored for 7 days, which would confirm results from our pilot study where we observed an 82% difference in proportional change between 7- and 42-day VO₂ max study arms. We will test the change scores for normal distribution, and will compare the 42- to 7-day groups using either a student's t-test or Wilcoxon rank sum test in a one sided superiority hypothesis test at the 0.05 significance level. Subjects who withdraw or are excluded before randomization will simply be dropped from analysis. We will further examine the treatment effect by adjusting for potential effects of hemoglobin, and BMI in a linear regression model.
- **Secondary outcomes:** Our secondary outcomes include mean proportional change between 7- and 28-day VO₂ max study arms, and change in duration of exercise between all three groups. Of note, in contrast to the primary endpoint, this secondary analysis is expected to show increases in VO₂ max attributable to intravascular volume expansion and increased hemoglobin mass. Nevertheless, these changes are of interest and it is possible that storage duration may affect VO₂ max acutely after transfusion.

Sample Size: Sample size and power are estimated for a superiority study design using a t-test with a power of 80%, and a one-sided significance level of 0.05. Based on the collected pilot data, we expect the mean percent change VO₂ max for subjects who receive 7-day blood to be 8.7% (SD = 6%), and the mean percent change VO₂ max for subjects who receive 42-day blood to be 1.6% (SD = 6%), providing an effect size of 1.183. Thus, the sample size needed for each group is 10 participants, for a study total of 30. While this calculated sample size may not allow us enough power to test a non-inferiority margin of 20% between the 7 day and 28 day groups, it will provide exploratory evidence for a future trial by providing a more accurate assessment in the variation of the data.

F. FUNDING STATUS, DETAILS

This study is funded by a grant from the National Institutes of Health/NHLBI.

G. HUMAN SUBJECTS RESEARCH PROTECTION FROM RISK

Risks to Subjects

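### The day stated for Cycle B's first blood draw fits neither the 28-day arm definition nor the recovery time given in the next sentence

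*Combined protocol and SAP*

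**What the plan says.** Section D.1 Overview defines the arms by the storage age of the transfused units: "Subjects will be randomized (1:1:1) to either cycle A (7 day RBCs), cycle B (28 day RBCs, or cycle C (42 day RBCs". It places baseline testing, transfusion and final testing on Monday, Wednesday and Friday of week 6 in every cycle. The transfused fraction in Section D.5 (Wednesday of Week 6) is tied to the same ages and includes "95% of 28-day RBCs".

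The readable text on draw timing is this:

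- Section D.1, removal of waste units: "Cycle A has 2 units removed at Week 0, Cycle C has 2 units removed at Week 5". Cycle B is not mentioned there.
- Section D.1, Blinding, on Cycle B: "their initial 2 unit phlebotomy will be at day 28 and not at day zero".
- The sentence after it: "They will have had 14 fewer days to recover hemoglobin compared to cycles A and C".
- Section D.5, heading on blood donation: "Visit B on Day 0, Visit C on Day 35".
- Subject Payment: a sum "for completing the day 40 exercise test visit". It is listed after the two donation visits and before the transfusion visit, so it is the Monday test.

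**The concern.** Storage age is the intervention in this trial, and for a given transfusion day it is fixed by the day of the draw. The Blinding paragraph is the only readable place that gives a day for Cycle B's first draw. Read on the study-day count used elsewhere, that day conflicts with the arm's definition and with the sentence beside it.

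Followed literally, it would give Cycle B a different storage age from the one Aim 2 is about, namely the 7- versus 28-day comparison meant to help explain RECESS. Other text depends on the same date:

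- The Blinding paragraph uses it to justify a one-unit second draw, and then expects pre-transfusion hemoglobin similar to the other cycles.
- Section G requires a bacterial test 7 days before re-infusion for blood stored more than 14 days. Units aged exactly 14 days would not trigger that rule; 28-day units would. Section D.5 separately calls for a culture of every unit.

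**Working it through.** **Step 1. Find the transfusion day from the protocol's own anchors.**

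| Anchor | Source | Calculation |
|---|---|---|
| Monday test is day 40; transfusion is on Wednesday | Subject Payment; D.1 | 40 + 2 = 42 |
| Cycle C's waste units leave at Week 5, so its 42-day units come from the Day 0 draw | D.1; D.5 heading | 0 + 42 = 42 |
| Cycle A's waste units leave at Week 0, so its 7-day units come from the Week 5 draw (5 × 7 = day 35) | D.1; D.5 heading | 35 + 7 = 42 |

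All three give study day 42.

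**Step 2. Reproduce the stated recovery difference.** If Cycle B's units are 28 days old at transfusion, the first draw is 28 days before transfusion, against 42 days for a day-zero draw. The difference is 42 − 28 = 14 days, exactly as stated. So the arm definition and the recovery statement agree.

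**Step 3. Put in the stated draw day.**

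- Storage age = transfusion day − draw day = 42 − 28 = 14 days, against the defined 28.
- Recovery deficit against day zero = 28 − 0 = 28 days, against the stated 14.
- Gap to the second draw = 35 − 28 = 7 days. A first draw that matches the 28-day age would leave 28 − 7 = 21 days.

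**Step 4. Try other readings of day 28.**

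- *Days before transfusion.* This gives 28-day units and a 14-day difference. But the same clause contrasts day 28 with day zero. On a countdown, day zero is the transfusion day, when no cycle draws units.
- *A clock that restarts at Cycle B's own first draw.* That draw would then be day zero, which the clause denies. Transfusion would fall on day 28 (28 / 7 = week 4), against week 6 for every cycle.

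**Step 5. Check the donation heading.** Draws on Day 0 and Day 35 give units aged 42 − 0 = 42 and 42 − 35 = 7 days at transfusion. Neither is 28.

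**Step 6. Check the primary comparison.** The sample-size inputs are 8.7% versus 1.6%, SD 6%, one-sided 0.05 and 80% power. The effect size is (8.7 − 1.6) / 6 = 1.183. Exact t-test power is 0.775 at 9 per group and 0.816 at 10, so the stated 10 per group reproduces. No input involves Cycle B's draw day.

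**The case against.** The best counter-argument is that the meaning is recoverable. Every arm is named by its storage age, 28 days is used consistently for Cycle B elsewhere, and the same paragraph counts back from the transfusion week when it describes the second draw. Day 28 may simply be shorthand for 28 days before transfusion, in which case one label is loose and no endpoint, test or sample size changes. This has force. It is why the point is put as a probable labelling slip and not as evidence that 14-day blood would be given. It does not clear the sentence, because the reading works only if one clause uses two different counts.

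A second argument is that the donation heading need not be a complete visit list, and that the design figure under Section D may show the missing draw. That stands as a limit: the omission can be stated only for the readable text. If the figure does give a day that fits 28-day storage, the sentence would then conflict with the figure as well.

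A third is that the affected comparison is secondary. The Sample Size paragraph concedes limited power for the 7- versus 28-day comparison and says of the planned sample that "it will provide exploratory evidence for a future trial". This limits the weight of the point, but exploratory evidence about 28-day blood still requires the schedule to specify that age.

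**Conclusion.** The inconsistency is real. On the protocol's own day count, the stated draw day implies a storage age of 14 days against the defined 28, and a recovery deficit of 28 days against the stated 14. One arm of three is concerned, 10 of 30 planned participants, and with it Aim 2. The primary 7- versus 42-day comparison, its significance level and its 10 per group are untouched.

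The conclusion assumes that the day 40 visit is the Monday test and that week 6 runs on the same count in every cycle; the text supports both. It does not depend on what the unseen figure shows. The point should be corrected, but it does not threaten the trial's main result.

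**What to change.** Reconcile Sections D.1 and D.5 and the Subject Payment text on a single day count starting at Day 0. Cycle B's draw day, its storage age at transfusion, the recovery-time sentence and the list of donation visits should then all agree, and agree with the design figure. Which day is intended is for the sponsor to state. The sponsor should also confirm that the expectation of similar pre-transfusion hemoglobin was worked out for the reconciled schedule.

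The cost is a wording correction to one sentence and one heading. It adds no procedures and does not change the sample size.
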